### **6.6.2      Excluded Medications**

Excluded medications include all steroid medications, other Ips, as well as ketoconazole, St. John's wort, and Chinese medicine therapies.

Concurrent use of adrenocorticotropic hormone (ACTH), prednisone or other glucocorticoid is not permitted, nor use of the strong inducers of cytochrome P450 3A4 (CYP3A4) (except approved ASMs: carbamazepine, phenytoin derivatives, phenobarbital, or primidone), rifampin, St. John's Wort, and Chinese medicine therapies.

Note: Concomitant intranasal or pro re nata (PRN) topical steroids for dermatologic reactions and allergic rhinitis are allowed.

Products containing tetrahydrocannabinol (THC) or non-approved CBD are excluded during treatment. THC or non-approved CBD should be washed out for at least 4 weeks prior to the initial visit. Participants with a positive result on THC or CBD laboratory tests during the parent study, and who do not have an explanatory Epidiolex®/Epidyolex® prescription, will not be eligible to participate in this OLE.

## **6.7 Intervention After the End of the Study**

Treatment can continue until the sponsor terminates this study.

# **7 DISCONTINUATION OF STUDY INTERVENTION AND PARTICIPANT DISCONTINUATION/WITHDRAWAL**

## **7.1 Discontinuation of Study Intervention**

In rare instances, it may be necessary for a participant to permanently discontinue study intervention. If the IP is discontinued at any time, participants should follow the 2-week taper schedule unless otherwise medically indicated such, as drug-induced rash. If the participant discontinues the IP, evaluations listed for the Early Termination Visit (Visit 13 [Week 156]; as shown in the SOA [Table 1]) are to be performed as completely as possible along with the end of study and safety follow-up assessment, as appropriate. Comments (spontaneous or elicited) or complaints made by the participant must be recorded in the source documents. The reason for termination, date of stopping IP, and total amount of IP taken must be recorded in the eCRF and source documents. Discontinuation of IP due to AEs must also be reflected on the AE eCRF page. Participants who discontinue IP should undergo a 2-week or shorter taper period, as clinically indicated. These participants will have a visit 2 weeks after the end of taper to complete the safety follow-up assessments.

The reason for early discontinuation of the IP must be determined by the investigator and recorded in the participant's source documents and on the eCRF. If a participant is withdrawn for more than 1 reason, each reason should be documented in the source document and the most clinically relevant reason should be entered on the eCRF.

Reasons for early termination include but are not limited to the following:

- AE (including pregnancy).
- Protocol violation/protocol deviation.
- Withdrawal by participant or parent(s)/LAR(s).
- Lost to follow-up.
- Lack of efficacy.
- Death.
- Investigator decision.

## 7.2 Discontinuation/Withdrawal from the Study

All participants or his/her parent(s)/LAR(s) reserve the right to withdraw from the study at any time, as stated in the informed consent/assent form. The investigator may discontinue participants from the clinical study for any of the following reasons:

- Participant is found to have entered the study in violation of the protocol.
- Participant requires the use of a disallowed concomitant medication.
- Participant's condition changes after entering the clinical investigation so that the participant no longer meets the inclusion criteria or develops any of the exclusion criteria.
- Participant or parent(s)/LAR(s) withdraws consent or assent to participate in the study.
- Participant is noncompliant with the procedures set forth in the protocol.
- Participant experiences an AE/SAE that warrants withdrawal from the study.
- Any laboratory, medical, or clinical finding for which clinical intervention should take precedence over study participation. This includes:
  - Aspartate aminotransferase (AST)/serum glutamic oxaloacetic transaminase (SGOT) or alanine aminotransferase (ALT)/serum glutamic pyruvic transaminase (SGPT)  $> 3 \times$  upper limit of normal (ULN).
  - Total bilirubin levels  $> 1.5 \times$  ULN.
  - Estimated glomerular filtration rate (eGFR)  $< 30$  mL/min.
- It is the investigator's opinion that it is not in the participant's best interest to continue in the study.

Decisions to discontinue the study will be made at each participating site by the investigator. If feasible, the reason for discontinuation should be discussed with the sponsor's medical monitor prior to participant's discontinuation.

At the time of discontinuing from the study, if possible, an Early Termination Visit (Visit 13 [Week 156]) should be conducted as shown in the SOA (Table 1). At this visit, participants will start a 2-week taper and then return to the site 2 weeks later for safety follow-up assessments.

If the participant withdraws consent for disclosure of future information, the sponsor may retain and continue to use any data collected before such a withdrawal of consent.

If a participant withdraws from the study, he/she may request destruction of any samples taken and not tested, and the investigator must document this in the site study records.

### **7.3 Lost to Follow-up**

A participant will be considered lost to follow-up if he/she repeatedly fails to return for scheduled visits without stating an intention to withdraw consent and is unable to be contacted by the study site.

The following actions must be taken if a participant fails to return to the clinic for a required study visit:

- The site must attempt to contact the participant and reschedule the missed visit as soon as possible, counsel the participant on the importance of maintaining the assigned visit schedule and ascertain whether the participant wishes to and/or should continue in the study.
- Before a participant is deemed lost to follow-up, the investigator or designee must make every effort to regain contact with the participant. A minimum of 3 documented attempts must be made to contact any participant lost to follow-up at any time point prior to the last scheduled contact (office visit or telephone contact). At least 1 of these documented attempts must include a written communication sent to the participant's last known address via courier or mail (with an acknowledgment of receipt request) asking that they return to the site for final safety evaluations and return any unused IP. If contact is made but the participant refuses or is unable to return to the site for the early termination and final safety follow-up visit, it should be documented in the eCRF.
- Should the participant continue to be unreachable, he/she will be considered to have withdrawn from the study.

Discontinuation of specific sites or of the study as a whole are handled in Section 10.1.9.

## **8 STUDY ASSESSMENTS AND PROCEDURES**

Study procedures and their timing are summarized in the SOA (Section 1.3). Study dates will be based on the date of the first dose of IP in this OLE and not the date of baseline visits.

Study assessments can be conducted at the institution of the site investigator or remotely at the participant's home. All assessments can be conducted remotely by the site staff using telemedicine video tools; and for sites located outside of the European Union only, by providing traveling nurses to take vital signs, draw blood samples, and collect specimens.

Immediate safety concerns should be discussed with the sponsor immediately upon occurrence or awareness to determine if the participant should continue or discontinue study intervention.

Adherence to the study design requirements, including those specified in the SOA, is essential and required for study conduct.

All evaluations must be completed and reviewed to confirm that potential participants meet all eligibility criteria. The investigator will maintain an enrollment log to record details of all participants from 1042-TSC-3001 and 1042-TSC-2001 studies who enter this OLE and to confirm eligibility or record reasons for participant exclusion, as applicable.

Procedures conducted in the parent study or as part of the participant's routine clinical management (eg, blood count) and obtained before signing of the ICF for the parent study may be utilized for baseline purposes provided the procedures met the protocol-specified criteria and were performed within the timeframe defined in the SOA.

## **8.1 General Study Periods**

### **8.1.1 Screening, Enrollment, Randomization, and Baseline**

There is no screening period in this OLE study. Participants from Study 1042-TSC-3001 and Study 1042-TSC-2001 will be enrolled in this OLE if eligible and continue maintenance treatment with GNX.

Note for Investigational Sites in the United Kingdom (UK): NHS sites in the UK will be aware of the study by virtue of the investigators participating in the site initiation visit, and being trained on the study design, conduct, and participant protection policies.

Informed consent/assent will be obtained after the study has been fully explained to the participant/parent(s)/LAR(s) and before the conduct of any assessments (Section 10.1.3 for the informed consent procedure). This will occur at the end of the double-blind treatment period in Study 1042-TSC-3001 and before any dose adjustments are made or prior to entry into the OLE for participants in Study 1042-TSC-2001.

#### **8.1.1.1 Demographics and Medical History**

Demographics including age, gender, ethnicity, and race, as allowed according to local regulations, will be collected in the parent study. In addition to the genetic evaluation of pathogenic or likely pathogenic TSC1/TSC2 variant, relevant medical history including but limited to the age of seizure onset, other physical disabilities such as scoliosis, visual impairment, sensory problems, and gastrointestinal difficulties will also be assessed in the parent study as will the participant's developmental history. This will include the grade level of schoolwork that the participant has completed (for individuals who are chronologically school age), as well as the investigator's estimate of the participant's developmental age.

Details of prior medications include all treatment, including but not limited to herbal treatments, vitamins, surgical implants (such as vagal nerve stimulator [VNS]), and prescribed medications, will be collected.

Demographics and Medical History will be reviewed at the end of the parent(s)/LAR(s) study/Visit 1 (First Visit of the OLE).

### **8.1.1.2 Seizure Identification and Diagnostic Review**

Per the inclusion criteria of the parent study, enrollment will be based on the presence and frequency of the seizure types defined as follows:

- Focal motor seizures without impairment of consciousness or awareness.
- Focal seizures with impairment of consciousness or awareness with motor features.
- Focal seizures evolving to bilateral, tonic-clonic convulsive seizures.
- Generalized motor seizures including tonic-clonic, bilateral tonic, bilateral clonic, or atonic/drop seizures.

Seizures must have a motor component sufficiently prominent and distinct to clearly establish the observed symptoms as epileptic in origin. Seizures that **do not count** towards efficacy endpoints include:

- Focal or generalized nonmotor seizures (eg, absence seizures or focal nonmotor seizures with or without impairment of awareness).
- Infantile or epileptic spasms.
- Myoclonic seizures.

To standardize seizure identification and classification in the study, a Seizure Identification Form/Diagnostic Review Form (SIF/DRF) will be submitted and reviewed by the Epilepsy Study Consortium prior to the participant's entry into the parent study and this information will be used in this OLE.

### **8.1.2 Open-label Treatment Phase**

Open-label treatment with the IP, at the dose determined in the parent study, will continue in this OLE. All dates during the open-label phase will be based off the date of the first dose of IP in the OLE.

Participants who discontinue the study prematurely before Visit 13 (Week 156) are required to taper their IP for 2 weeks or shorter, unless otherwise medically indicated. Participants should also complete the eDiary during this time. The end of study assessments, as detailed in the SOA for Visit 13 should then be performed (Table 1).

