## Overall Design:

This is a Phase 3, global, OLE study of adjunctive GNX treatment in children and adults with TSC who previously participated in either Study 1042-TSC-3001 or Study 1042-TSC-2001. For this protocol, the term children will refer to the full range of pediatric participants.

For all participants who enter the OLE, the last visit in the parent Study 1042-TSC-3001 or Study 1042-TSC-2001 will be the same as the First Visit in this OLE study and visit activities will not be duplicated.

Procedures specific to this protocol and not otherwise considered standard of care, will not be performed until written informed consent/assent from the participant or their parent(s)/legally authorized representative(s) (LAR[s]), as appropriate, has been appropriately obtained.

Participants or their parent(s)/caregiver(s) or LAR(s) are expected to complete electronic seizure diary (eDiary) entries to document the number and type(s) of seizures daily throughout the first year of the study. After the first year, study assessments will focus on safety evaluation. Caregiver and clinician global impressions of improvement will continue to be assessed to ensure that participants are continuing to receive benefit from treatment. A variety of clinician and caregiver administered instruments will be used to assess efficacy at the study visits including:

- Clinical Global Impression of Improvement (CGI-I) by parent(s)/caregiver(s) and clinician.
- Caregiver Global Impression of Change in Seizure Intensity/Duration (CGI-CSID).

- Short Form 36 (SF-36) (first year of the study only).

Safety monitoring and assessments will be conducted throughout the study.

The maximum dose for all participants is 1800 mg/day.

Participants who discontinue the investigational product (IP) should undergo a 2-week taper period. The taper period may be shortened, if necessary, for participant safety. Participants who discontinue the IP before the scheduled completion of the study will have an Early Termination Visit, as per Visit 13 (Week 156), and return to the site 2 weeks after the end of the taper period to complete the safety follow-up assessments.

The study design is presented in Figure 1.

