ASM = anti-seizure medication; BP = blood pressure; CGI-CSID = Caregiver Global Impression of Change in Seizure Intensity/Duration; CGI-I = Clinical Global Impression of Improvement; C-SSRS = Columbia-Suicide Severity Rating Scale; eCRF = electronic case report form; ECG = electrocardiogram; ET = early termination; HR = heart rate; IP = investigational product; LAR = legally authorized representative; OLE = open-label extension; PK = pharmacokinetic; QOL = quality of life; RR = respiratory rate; SF-36 = Short Form 36 (version 2); WOCBP = women of childbearing potential.

- a Any data collected at the final visit of the parent study will be carried over to Study 1042-TSC-3002. Any procedures not performed at the final visit of the parent study will be conducted at Visit 1 on Day 1 of this study.
- b It is estimated that the maximum duration of participation in this OLE study will be approximately 3 years.
- c For participants who discontinue treatment, either early, or at Visit 13 (Week 156) and prior to down-titration unless medically indicated.
- d Demographics and medical history will be reviewed to confirm there are no changes from the parent study.
- e Hematology, clinical chemistry, and urinalysis (see Section 8.3.4).
- f A serum pregnancy test is required for all WOCBP at Visit 1 on Day 1 of this OLE study. Urine pregnancy testing will then be performed every 4 weeks throughout the OLE using take-home pregnancy tests. Any positive home pregnancy test will be followed up with a confirmatory serum pregnancy test.
- g Population PK will be conducted at Visit 3 and Visit 5 and the PK sample can be drawn when convenient during the specified study visit.
- h If the levels of ASM co-administered with the IP are measured routinely, this information will be recorded in the eCRF.
- i Only for participants  $\geq$  11 years of age, if appropriate, otherwise, clinical judgment will be used.

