## 4 STUDY DESIGN

### 4.1 Overall Design

This is a Phase 3, global, OLE study of adjunctive GNX treatment in children and adults with TSC-related epilepsy who previously participated in either Study 1042-TSC-3001 or Study 1042-TSC-2001. For this protocol, the term children will refer to the full range of pediatric participants.

For all participants who enter the OLE, the last visit in the parent Study 1042-TSC-3001 or Study 1042-TSC-2001 will be the same as the First Visit in this OLE study and visit activities will not be duplicated.

Procedures specific to this protocol and not otherwise considered standard of care, will not be performed until written informed consent/assent from the participant or their parent(s)/LAR(s), as appropriate, has been appropriately obtained.

Participants or their parent(s)/caregiver(s)/LAR(s) are expected to complete electronic seizure diary (eDiary) entries to document the number and type(s) of seizures daily throughout the first year of the study. After the first year, study assessments will focus on safety evaluation.

Caregiver and clinician global impressions of improvement will continue to be assessed to ensure that participants are continuing to receive benefit from treatment. A variety of clinician and caregiver administered outcome measures will be used at the study visits to assess efficacy. These include:

- Clinical Global Impression of Improvement (CGI-I) by parent(s)/caregiver(s) and clinician.
- Caregiver Global Impression of Change in Seizure Intensity/Duration (CGI-CSID).

- Short Form 36 (SF-36) (first year of the study only).

Safety monitoring assessments will be conducted throughout the study.

The maximum dose for all participants is 1800 mg/day.

Participants who discontinue the investigational product (IP) should undergo a 2-week taper period. The taper period may be shortened, if necessary, for participant safety. Participants who discontinue the IP before the scheduled completion of the study will have an Early Termination Visit, as per Visit 13 (Week 156), and return to the site 2 weeks after the end of the taper period to complete the safety follow-up assessments.

The study design is presented in Figure 1.

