### **8.1.3 Safety Follow-up**

A safety follow-up visit will be conducted at Visit 14 (Week 160), which will be 2 weeks after the end of the 2-week taper for participants who are not continuing commercially available GNX (Table 1). This will be the end of study visit for these participants.

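### For early discontinuers, Protocol 8.1.2 puts the Early Termination assessments after the taper, while SoA footnote c and 7.2 put them before it, so the same assessments may be on-drug or off-drug

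*Protocol*

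**What the plan says.** Two places put the ET visit before the taper. Footnote c to Table 1 (SoA) describes the Visit 13/ET column this way: "For participants who discontinue treatment, either early, or at Visit 13 (Week 156) and prior to down-titration unless medically indicated". Protocol 7.2, on the ET visit, says: "At this visit, participants will start a 2-week taper and then return to the site 2 weeks later for safety follow-up assessments".

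One place puts it after. Protocol 8.1.2 opens with "Participants who discontinue the study prematurely before Visit 13 (Week 156) are required to taper their IP for 2 weeks or shorter" (subject to medical need), asks for diary entries during that time, and continues: "The end of study assessments, as detailed in the SOA for Visit 13 should then be performed".

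Other passages lean one way or leave the order open. Section 4.1 says that participants who stop early "will have an Early Termination Visit, as per Visit 13 (Week 156), and return to the site 2 weeks after the end" of the taper; the Synopsis has the same text. This names the ET visit first but does not say when it falls relative to the start of the taper. Section 7.1 says the ET evaluations "are to be performed as completely as possible along with the end of study and safety follow-up assessment, as appropriate", which does not settle the order. Section 8.1.3 times Visit 14 (Week 160) as a visit "which will be 2 weeks after the end of the 2-week taper".

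The SAP introduction describes the ET visit as matching Visit 5 (Week 52), not Visit 13 (Week 156). The SAP has no rule that separates ET records taken before the taper from those taken during or after it.

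**The concern.** An assessment at the last full dose and one taken after the drug has been withdrawn answer different questions. The first describes the participant under treatment at the time of stopping; the second describes early recovery or withdrawal. If the protocol allows either, the ET record has no fixed meaning, and it belongs to the participants who say most about tolerability.

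The point matters most where the ET visit is the last collection. If 8.1.2 is followed, there may be no scheduled laboratory sample near the end of full-dose exposure, and no later analysis can supply one. The order also affects the diary: if the ET visit closes the open-label period and follows the taper, taper days fall inside that period.

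**Working it through.** **1. The passages side by side, for a participant who stops before Week 156**

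| Place in the protocol | ET assessments relative to the taper |
|---|---|
| SoA (Table 1), footnote c | Before, with an exception for medical need |
| 7.2 | Before: the taper starts at the visit |
| 1.1 and 4.1 | ET named first; order only implied |
| 7.1 | Not settled |
| 8.1.2 | After |

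**2. The plan's own figure.** Visit 14 is at Week 160. Week 156 (Visit 13) + 2 weeks of taper + 2 weeks = Week 160, which reproduces it. Visit 13 thus precedes the taper for scheduled completers. The sentence in 8.1.2 covers only those who stop before Visit 13, so completers are not in conflict.

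**3. Timeline for an early discontinuer.** Let week 0 be the start of stopping, with a full 2-week taper.

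- Footnote c and 7.2: ET at week 0, taper from week 0 to 2, follow-up at 2 + 2 = week 4. Gap from ET to follow-up: 4 − 0 = 4 weeks.
- 8.1.2: taper from week 0 to 2, ET at about week 2 or later, follow-up at week 4. Gap: 4 − 2 = 2 weeks or less.

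The ET assessments move by about 2 − 0 = 2 weeks, from on-drug to off-drug. With a shorter taper the move is correspondingly shorter.

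The follow-up wording in 7.2 can be counted in two ways. From the ET visit it gives week 2, the day a full taper ends. From the end of the taper it gives week 4, in line with 1.1, 4.1, 7.1 and 8.1.3.

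**4. Which measures depend on the order** (SoA; Protocol 8.2.2, 8.2.3, 8.3.1 to 8.3.5, 8.4.1)

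| Measure | At Visit 13/ET | At Visit 14 | Consequence |
|---|---|---|---|
| Laboratory tests (primary) | Yes | No | Last value on-drug or off-drug |
| CGI-I, CGI-CSID (secondary) | Yes | No | Last rating on-drug or off-drug, if ET ratings count |
| Vital signs, examinations, C-SSRS | Yes | Yes | Only the ET value is ambiguous |
| ECG | No | Yes | None |
| Adverse events | Collected throughout | Yes | Incidence does not hinge on the ET date |

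**5. What the SAP does with these records.** SAP 4.3.2 treats every laboratory value after the first dose as post-baseline. SAP 5.2 summarises safety data by actual visit without windows. SAP 5.7 ends treatment on the last day drug was taken, so taper days count as treatment days there. SAP 5.2 runs the open-label period to Visit 13, and SAP 4.4.1 and 4.4.5 use all open-label diary days with data. Taper days are not set apart in any of these.

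**6. Size of the diary effect.** A full taper adds 2 × 7 = 14 diary days. Suppose full dosing ran for d days from the first extension dose (the starting point in Protocol 9.2.6) and the diary is complete. The taper share of diary days is then 14 / (d + 14). At the Year 1 visit weeks:

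- Week 13, d = 91: 14/105 = 13.3%
- Week 26, d = 182: 14/196 = 7.1%
- Week 39, d = 273: 14/287 = 4.9%

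With share s, the reported 28-day rate is (1 − s) × the full-dose rate + s × the taper rate. The documents give no taper-period rate, so the shift in the rate cannot be computed. Only Year 1 stoppers matter here, because the seizure endpoints are confined to the first year.

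**The case against.** The strongest reply is that 8.1.2 itself sends the site to Table 1, that footnote c there fixes the order, and that Section 8 makes adherence to the SoA mandatory. That lowers the practical risk. It does not remove the conflict, because footnote c contradicts the sequence in the very section that points to it. Footnote c also allows a medical exception, so some ET visits could fall after the taper has begun even under its own rule.

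A reader might infer that 7.2 contradicts the other sections on follow-up timing. The documents do not support that: read in sequence, 7.2 can mean taper first and then a further 2 weeks, which agrees with them. The wording is ambiguous, not contradictory.

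A reader might also infer that the primary safety endpoints as a whole are blurred. The table in the working shows otherwise. Among the primary measures only laboratory tests have their last scheduled collection at ET, and their shift tables use the worst post-baseline classification, which dilutes the weight of any one visit.

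The CGI consequence is conditional. The CGI-I endpoint is defined at the last scheduled visit, SAP 5.2 limits efficacy analyses to scheduled visits, and the SAP does not say whether an ET rating qualifies.

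Finally, dosing dates are recorded and the study is purely descriptive, so drug status at ET can be recovered. That is true for classifying records already taken, but not for a sample that was never drawn on full dose.

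**Conclusion.** The inconsistency stands, in current protocol text. For early discontinuers, footnote c and 7.2 put the ET assessments before the taper and 8.1.2 puts them after it, a difference of about 2 weeks with a full taper. The direct effect is limited to ET laboratory tests, to CGI-I and CGI-CSID if ET ratings count, and to up to about 14 diary days for each participant who stops in Year 1. Those days could enter the seizure rate, responder status and seizure-free days.

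It is tempting to conclude that ET data are on-drug at some sites and off-drug at others. The documents show only that the wording permits this, not that it has happened. Nor can a count be given. Neither document states or assumes a discontinuation rate for this extension, so any percentage of the planned enrolment (169 in the protocol, 150 in the SAP) would be a guess. Only participants whose ET visit is actually held after the taper starts would have shifted data.

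The per-participant sizes assume a full 2-week taper and, for the diary shares, complete entries. This review takes no position on which order is right.

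**What to change.** **Protocol.** Reconcile SoA footnote c, 7.1, 7.2 and 8.1.2 to one order of taper, ET visit and follow-up visit. In the same edit, say whether the 2 weeks in 7.2 run from the visit or from the end of the taper.

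**SAP.** Align the introduction, which ties ET to Visit 5 (Week 52), with the protocol's Visit 13 (Week 156). Class each ET assessment and each diary day as on-treatment, taper or off-treatment from the eCRF dosing dates. Present taper and off-treatment records separately from the on-treatment laboratory, CGI and seizure-frequency summaries. State whether an ET rating enters the CGI-I and CGI-CSID endpoints.

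**Cost.** One protocol clarification and one SAP derivation. No new data are needed: Protocol 6.5 already records start and stop dates and dose reductions in the eCRF, and SAP 5.7 already lists daily dose with dates and reasons for change. The SAP rule can also be applied to data already collected.
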